APPENDIX B: HIV TESTING ALGORITHM

Figure 1: Screening Algorithm

[figure not shown]

Figure 2: Pre-Enrolment Algorithm

[figure not shown]

Figure 3: Trial Visits Algorithm

[figure not shown]

Figure 4: LPUV Algorithm

[figure not shown]
[figure not shown]

Figure 5: Exit Visit Algorithm

APPENDIX C: VISIT SCHEDULE AND APPROXIMATE BLOOD VOLUMES

Visit	Test and volume (mL)	Test and volume (mL)	Test and volume (mL)	Test and volume (mL)	Test and volume (mL)	Total Blood Volume
Screening	HIV rapid* 5 mL		Chemistry 5 mL Haematology 5 mL RPR 5 mL	HIV viral genotype resistance [#] 10 mL	HIV PCR# 5 mL	35mL
Enrolment	HIV rapid 5 mL			HIV viral genotype resistance [#] 10 mL	HIV PCR# 5 mL	20 mL
Trial Visits	HIV rapid 5 mL	Dapivirine levels [#] 6 mL		HIV viral genotype resistance [#] 10 mL	HIV PCR# 5 mL	26 mL
LPUV	HIV rapid 5 mL	Dapivirine levels [#] 6 mL		HIV viral genotype resistance [#] 10 mL	HIV PCR# 5 mL	26 mL
Exit Visit	HIV rapid [^] 5 mL			HIV viral genotype resistance ^{##} 10 mL	HIV PCR#/## 5 mL	5 mL or 15 mL##
Seroconverter tests⁺	Western blot 5mL	Dapivirine levels ⁺⁺ 6 mL		HIV viral genotype resistance [#] 10 mL	HIV PCR# 5 mL	20 mL ⁺⁺ or 26 mL

- * Depending on the research centre SOP on HIV testing, sampling may be performed by finger prick or venepuncture.
- # Stored plasma samples; tested retrospectively to evaluate different parameters at the time of seroconversion.
- ## Blood samples for viral genotype resistance and HIV-1 RNA PCR testing will be collected at the scheduled exit visit following seroconversion.
- ^ HIV rapid testing will not be conducted at the scheduled exit visit following seroconversion.
- + At the point of seroconversion, these samples will be collected and tested in addition to relevant visit-specific tests, but no samples should be duplicated during the same visit. No additional storage samples will be collected.

NOTE: Additional tests may be also performed, as required.

- ++ Test sample for possible dapivirine measurements will not be required if the seroconversion occurs at the Exit Visit.

APPENDIX D: TRIAL DESIGN

1. INTRODUCTION

This document serves as the Statistical Analysis Plan (SAP) for the protocol pre-specified primary, secondary and exploratory endpoints for IPM 032, the Phase IIIb follow-on trial to IPM 027. Specifically, this document describes the statistical methods that will be used to analyse the final data from IPM 032 to support the completion of the Clinical Study Report (CSR). The planned analyses described in this SAP will form the basis for the assessment of safety and adherence to the use of the Dapivirine Vaginal Ring-004, as determined in the follow-on trial, and will be included in regulatory submissions and/or future manuscripts. Also, exploratory analyses not necessarily identified in this SAP may be performed.

Table shells, example figures, and listing shells that will accompany the analysis are provided in Appendices 1, 2, and 3, respectively. The appendices are viewed as supporting material of the analysis and will not require signature approval if formatting changes are made.

This document is based on the current version of the IPM 032 trial protocol, Version 2.0, Amendment 2.0, which was approved on 16 January 2017. However, due to changes in the global donor environment, not all planned changes from protocol Version 2.0, Amendment 1.0 (dated 22 October 2015) were implemented. The sections in protocol Version 2.0, Amendment 2.0 that have been implemented are detailed in Appendix 6.

This analysis plan refers to Case Report Forms (CRFs) Version 1.0, dated 16 May 2016, and additional CRFs for capturing screen failure information (Version 2.0, dated 23 May 2016). The following CRFs were updated during the trial:

- Contraceptive/menstrual/obstetric history (CMO) CRF, end of trial inventory (ETI) CRF, menses information and pregnancy test results (PTR) CRF, pregnancy outcome 1 (PO1) CRF, ring insertion/removal (RL) log CRF, and HIV seroconversion evaluation (SERCON) CRF (Version 1.0, dated 16 May 2016, and Version 2.0, dated 27 April 2017 used starting 16 October 2017).

The following CRFs were developed during the course of the trial and implemented as indicated:

- Narrative log (NARR) CRF, returned ring log (RRL) CRF, seroconversion – HIV RNA PCR testing (SER PCR) CRF, and screening and enrollment (SEL) log CRF (Version 1.0, dated 27 April 2017 implemented starting 16 October 2017); participant transfer (PTRAN) CRF (Version 1.0, dated 28 June 2017, implemented

starting 20 July 2017); and participant receipt (PREC) CRF (Version 1.0, dated 28 June 2017, implemented starting 15 August 2017).

2. TRIAL OBJECTIVES

2.1 Primary Objectives

The primary trial objectives are:

- To assess the safety profile of the 25 mg Dapivirine Vaginal Ring-004, when inserted at monthly intervals, in an open-label trial.
- To assess adherence to the use of the 25 mg Dapivirine Vaginal Ring-004 inserted at monthly intervals, in an open-label trial.

2.2 Secondary Objectives

The secondary trial objectives are:

- To assess the incidence of HIV-1 seroconversion.
- To assess the frequency of HIV-1 drug resistance in women who acquire HIV-1 infection.

2.3 Exploratory Objectives

The exploratory trial objectives are:

- To assess the feasibility of 3-monthly follow-up visits, as a possible schedule for post-licensure vaginal ring clinical follow-up.
- To explore the correlation between drug concentrations and results from the visual inspection of the returned vaginal rings by research staff between the monthly and 3-monthly research centre follow-up schedules.
- To determine the proportion of participants electing to undergo HIV rapid tests at the research centres between scheduled 3-monthly visits.
- To characterize the IPM 027 participants who decline enrollment into IPM 032 (Decliner Population) [***Not implemented.***]
- To explore self-reported acceptability of and adherence to the 25 mg Dapivirine Vaginal Ring-004.

Note: Objectives indicated as “Not implemented” above, are not addressed in this analysis plan.

2.4 Assessment of Objectives

Consistent with the primary objectives, the **primary endpoints** are:

Safety

- All Adverse Events (AEs) assessed by the investigator to be related to the Dapivirine Vaginal Ring-004.

- All Grade 3 and 4 AEs.
- All Serious Adverse Events (SAEs).

Adherence

Residual amounts of dapivirine in returned rings and/or dapivirine concentrations in plasma and/or dapivirine concentrations in vaginal fluid.

The primary endpoints will be assessed through:

Safety

All product-related AEs, Grade 3 or 4 AEs, SAEs, physical examination, gynaecological assessments, including pelvic/speculum examination, laboratory tests and other indicated investigations.

Adherence

- Determined dapivirine residual amounts in returned used vaginal rings and/or
- Measured concentrations of dapivirine in plasma [**Not implemented**] and/or
- Measured concentrations of dapivirine in vaginal fluids [**Not implemented**.]

Consistent with the secondary objectives, the **secondary endpoints** are:

- The HIV-1 seroconversion rate per 100 woman-years of product use at the end of the vaginal ring use period.
- HIV-1 drug resistance mutations among participants who acquire HIV-1 infection.

The secondary endpoints will be assessed through:

- Rapid and specialised laboratory testing according to a pre-specified HIV testing algorithm.
- Viral genotype resistance testing methods which include sensitive methods to detect low frequency drug-resistant variants (only population genotyping will be done.)

Consistent with the exploratory objectives, the **exploratory endpoints** include:

- Feasibility of a 3-monthly clinical follow-up schedule.
- Dapivirine residual amounts in returned used vaginal rings and/or dapivirine concentrations in plasma and/or vaginal fluid in correlation with results from the visual inspection of the returned used vaginal rings by research staff.
- Proportion of participants opting for HIV rapid tests at the research centre between scheduled 3-monthly research centre follow-up visits.
- The proportion of women who report the use of the vaginal ring as acceptable.
- Participant self-reported patterns of ring use.

The exploratory endpoints will be assessed through:

- Participant report of feasibility regarding a 3-monthly clinical follow-up schedule (Participant Questionnaire).
- Number of women opting not to receive two additional rings at the 3-monthly visits.
- Proportion of returned rings (used and unused) during the 3-monthly clinical follow-up schedule.
- Dapivirine residual amounts in returned used vaginal rings and/or dapivirine concentrations in blood and/or vaginal fluid.
- Visual inspection of the returned used vaginal rings by research centre staff.
- Number of participants undergoing HIV rapid tests at the research centre between scheduled 3-monthly research centre follow-up visits.
- Qualitative data regarding ring acceptability and self-reported patterns of ring use.

Note: Although collected and stored, blood and vaginal fluid samples were not analysed for dapivirine, as dapivirine concentrations were found in the Phase III program to have limited value as adherence measures. There is currently no biomarker to indicate whether the ring was used at the time of an HIV risk event; the best measure of ring use during the prescribed 1-month use period is dapivirine ring residual levels in used rings.

3 TRIAL DESIGN

3.1 General Design and Plan

IPM 032 is a Phase IIIb, multi-centre follow-on open-label trial to evaluate the continued adherence to and safety of the Dapivirine Vaginal Ring-004 inserted at monthly intervals in healthy, HIV-negative women who have participated in the IPM 027 Phase III Dapivirine Vaginal Ring-004 trial. All women who have participated in IPM 027 and are HIV-negative at screening for IPM 032, will be eligible. It was estimated that approximately 1400 participants will be enrolled.

All participants will attend a research centre follow-up visit one month after enrollment. Following this visit, at the investigator's discretion, a participant can continue on a 3-monthly visit schedule. Monthly visits may however be extended up to the first three months of participation. Once the 3-monthly trial visit schedule commences, three rings will be dispensed to the participant. One ring will be self-inserted at the research centre and two additional rings will be dispensed for the participant to take home, or dispensing will take place as arranged with the participant.

Each participant will engage in the screening process for up to 45 days prior to enrollment and will use the Dapivirine Vaginal Ring-004 for a period of up to 12 months. IPM will have the option to extend this trial period. Accrual was expected to take place over approximately 6 months; participants enrolled more than 6 months after the onset of the study site's accrual period may have a shortened follow-up period.

Each participant will have an exit visit 1 to 2 months after ring discontinuation, to assess safety and identify HIV-1 seroconversions after product discontinuation.

3.2 Sample Size

This is an open-label, follow-on trial to IPM 027 to evaluate the safety of and adherence to the Dapivirine Vaginal Ring-004, inserted at monthly intervals in healthy, HIV-negative women who have participated in the IPM 027 trial. No formal sample size or power calculations have thus been performed. It was expected that approximately 70% of the participants enrolled in IPM 027 will participate in this trial. Therefore, a total sample size of approximately 1400 HIV-negative women was anticipated.

3.3 Randomisation

This is an open-label, follow-on trial. No randomisation will be done.

3.4 Blinding

This is an open-label study. No blinding will be performed.

4 SEQUENCE OF PLANNED ANALYSES

4.1 Safety Monitoring

Safety data from the trial were to be evaluated by an independent Data and Safety Monitoring Board (DSMB). The first scheduled meeting was to take place approximately six months after all research centres had been activated; subsequent meetings were held at approximately annual intervals for the duration of IPM 032. Based on the review of the data, the DSMB was required to provide recommendations about continuation, pausing, termination or other modifications to the trial, including changes to the information provided to participants for obtaining their informed consent. An IPM 032 DSMB charter was developed to describe the roles and responsibilities of the DSMB, its composition, data to be provided to the DSMB, the process for disseminating trial data to the DSMB, and the communication plan between the DSMB and IPM.

4.2 Interim Analyses

No interim analysis was planned for this trial. However, the Sponsor reviewed the treatment emergent safety data at regular intervals during the conduct of the trial.

Note: Although no formal interim analysis was planned or conducted for IPM 032, two summary reports of available data as of 30 April 2018 and 08 November 2018, respectively, were prepared and submitted to the European Medicines Agency (EMA), in response to requests by EMA during their review of the Dapivirine Vaginal Ring Article 58 application.

4.3 Final Analysis and Reporting

This SAP will be approved before final database lock. All final and planned analyses identified in the protocol and in this SAP will be performed only after the database has been locked. A review of the data will be performed prior to database lock for data quality purposes and for classification of protocol deviations as minor or major.

5 ANALYSIS POPULATIONS

Four analysis populations have been defined for this trial: a Safety population, Modified Intent-to-treat (m-ITT) population, Virology population and a Per-protocol (PP) or Protocol-adherent population. The number of participants valid for each population, and when appropriate, the reasons for excluding trial participants from these populations, will be presented overall and by research centre using relevant summary statistics.

5.1 Safety Population

The safety population will include all participants who were enrolled, and received and inserted at least one Dapivirine Vaginal Ring

5.2 Modified Intent-to-Treat (m-ITT) Population

Some participants recently infected with HIV-1 may not yet have detectable levels of HIV-1 antibodies at the enrollment visit, and therefore, HIV-infected women who are assumed to be HIV-negative may be enrolled in the trial. To accommodate this situation, an m-ITT population will be determined and used for the analysis of HIV-1 seroconversion rate. This population will exclude all participants who are included in the safety population but who were found to have been HIV-1 infected at the enrollment visit (*i.e.* women who have seroconverted after enrollment but were retrospectively found to be HIV-1 RNA positive at enrollment).

Virology Population

The virology population includes all participants in the m-ITT population, with the exception of those participants who seroconverted after the last product use visit (LPUV). That is, women who were still HIV-1 RNA negative at LPUV, and who became infected after discontinuation of ring use, will be excluded. Genotypic analyses from the small numbers of participants with infection at enrolment, or with no detectable HIV-1 RNA at the LPUV but with seroconversion at the Exit visit, will be described separately.

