6.5 Planned Subgroups, Interactions, and Covariates

The analysis of the HIV-1 seroconversion rate will be based on the m-ITT population, and the primary virology analysis of drug resistance will be based on the virology population. It is expected that women with pre-existing conditions (e.g. women with STIs at Screening) will be treated and evaluated before or at enrolment into the trial, therefore no baseline adjustments are planned prospectively; however, all data will be reviewed to assess any potentially relevant baseline imbalances between research centres.

Unless specified otherwise, statistical models will include research centre as main effect. Kaplan-Meier survival curves will be produced overall and by research centre, if possible.

The following subgroup analysis will be performed for the primary safety endpoint (AEs related to Investigational Product (IP), Grade 3 and 4 AEs and SAEs):

1. Participants in the age group < 25 years, and \geq 25 years

The following subgroup analysis will be performed for the primary adherence endpoint (residual amounts of dapivirine in returned rings):

1. Participant age at baseline (< 25 *versus* ≥ 25 years)
2. Marital status at baseline (married *versus* not married)
3. Has a main sex partner at baseline (yes *versus* no)
4. Presence of genital symptoms/Sexually Transmitted Infections (STIs) at baseline (yes *versus* no)

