9.3.2 Secondary Endpoint 2: HIV-1 drug resistance mutations among participants who acquire HIV-1

Consistent with the secondary objective to evaluate HIV-1 drug resistance mutations among participants who acquire HIV-1 in the trial, secondary endpoint 2 is the proportion of HIV-1 seroconverters with drug resistant mutations.

Assessments

HIV viral genotyping will be performed on all HIV-1 seroconverters.

Statistical methods

The analysis of HIV-1 drug resistance will be primarily descriptive in nature, and will depend on the pattern of resistance-associated mutations (RAMs) observed in the HIV-1 seroconverters. The Stanford NNRTI Resistance Mutation Scores of Drug Resistance Mutations in HIV-1 (database version 8.4 - dated 2017-06-16) is provided in Appendix 4.

The number of RAMs observed will be listed by participant, and a frequency tabulation of individual RAMs associated with the various classes of antiretrovirals (Protease Inhibitors [PIs], Nucleoside Reverse Transcriptase Inhibitors [NRTIs] and Non-nucleoside Reverse Transcriptase Inhibitors [NNRTIs]) will be produced. The proportion of HIV-1 seroconverters with at least one HIV-1 drug resistant mutation will be presented overall, and by research centre, if possible, with corresponding 95% confidence intervals (using the Fisher's exact test).

If the data allows, the following frequency tabulations will be created:

- The number (and percentage) of participants who had a resistance test performed (pre-seroconversion, at seroconversion and at the Exit visit.)

- Reasons why a resistance test was not performed (if available in the database.)
- The number (and percentage) of participants with each individual mutation by class (NNRTI, NRTI, major PI.)
- The number (and percentage) of participants with 0, 1, 2, and ≥ 3 mutations by class (NNRTI, NRTI, major PI.)
- The number (and percentage) of participants with different mutational patterns (including single mutations), by class (NNRTI, NRTI, major PI.)
- Additional mutations (e.g. those selected by dapivirine in vitro but not included in the Stanford HIV database set) will be described.

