In addition, for each NNRTI drug, the resistance mutation scores for NNRTIs efavirenz, etravirine, nevirapine and rilpivirine, will be calculated according to the Stanford database version 8.4, dated 2017-06-16 (see Appendix 4), per genotype by summing the individual scores associated with individual mutations (and the additional scores for combinations of mutations where applicable.) Based on the resistance mutation score, virus from participants will be classified as susceptible, potential low-level resistant, low-level resistant, intermediate resistant or high-level resistant for each NNRTI drug, based on the following cut-offs:

NNRTI resistance mutation score	Level of resistance
<10	Susceptible
10 - <15	Potential low-level resistant
15 - < 30	Low-level resistant
30 - < 60	Intermediate resistant
≥ 60	High-level resistant

For each approved NNRTI drug (efavirenz, etravirine, nevirapine and rilpivirine), descriptive statistics will be presented on the total NNRTI resistance mutation score and a frequency tabulation will be presented on the resistance level.

Note: Only results at time of HIV-1 seroconversion will be included in tabulations. Listings of all individual data will be created and will include all participant resistance assessments.

These analyses will be performed overall, by HIV-1 RNA level at HIV-1 seroconversion (≥ 2000 copies/mL, < 2000 copies/mL), treatment schedule (A, B or C) and by HIV-1 subtype (C, other).

There will be an additional analysis to determine the number and timing of samples analysed prior to and after HIV-1 seroconversion. Any changes of genotype between the prior- and after- HIV-1 seroconversion samples will be described.

Finally, the primary analysis will be repeated for the Virology Population, for all samples analysed at any time during the period of the first positive HIV-1 RNA visit and the Exit visit. This is to ensure that all mutations are accounted for.

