- **Table 14.7.10.2** will be similar to **Table 14.7.10.1** but the heading and analysis will be based on Any Timepoint

HIV-1 = Human immunodeficiency virus type 1; NNRTI = Non-nucleoside reverse transcriptase inhibitor ; NRTI = Nucleoside reverse transcriptase inhibitor; PI = Protease inhibitor
 Percentages are calculated out of the number of participants (per IPM 027 treatment) ^a In the virology population ^b Successful results

^c Resistance-associated mutations of interest not present in the data set are not included in the table

Resistance-associated mutations were defined using the Stanford HIV database algorithm Version 8.

Table 14.3.7.11
Data Overview of HIV-1 Seroconversion Timing Relative To HIV-1 RNA Detection and Treatment
Virology Population

Statistic	IPM 027 Dapivirine (N=XXX)	IPM 027 Placebo (N=XXX)	IPM 032 Overall (N=XXX)
First positive HIV-1 RNA Timing			
At time of seroconversion	n (%) ^a	X (X.X)	X (X.X)
Mutations detected before seroconversion	n (%) ^b	X (X.X)	X (X.X)
Mutations detected at seroconversion	n (%) ^b	X (X.X)	X (X.X)
Mutations detected after seroconversion	n (%) ^b	X (X.X)	X (X.X)
Before seroconversion			
At time of seroconversion	n (%) ^a	X (X.X)	X (X.X)
Mutations detected before seroconversion	n (%) ^b	X (X.X)	X (X.X)
Mutations detected at seroconversion	n (%) ^b	X (X.X)	X (X.X)
Mutations detected after seroconversion	n (%) ^b	X (X.X)	X (X.X)
Average days	Mean	XX.X	XX.X
Minimum and maximum days	(Min,Max)	(XX, XX)	(XX, XX)
IP use stopped			
At time of seroconversion	n (%) ^a	X (X.X)	X (X.X)
After seroconversion	n (%) ^a	X (X.X)	X (X.X)
Before seroconversion	n (%) ^a	X (X.X)	X (X.X)

Programmers Note: In case the date of last investigational product exposure (i.e. last ring removal) is missing, it is imputed with the last ring insertion date.

HIV-1 = Human immunodeficiency virus type 1

Percentages are calculated out of the number of participants (per IPM 027 treatment) ^a In the virology population ^b At the applicable visit

Table 14.3.7.12
 Overview of HIV-1 RNA and Genotyping Information Availability
 Virology Population

Statistic	IPM 027 Dapivirine (N=XXX)	IPM 027 Placebo (N=XXX)	IPM 032 Overall (N=XXX)
HIV-1 RNA for participants with HIV-1 seroconversion			
Participants with assessment prior to seroconversion	n (%) ^a	X (X.X)	X (X.X)
No HIV-1 RNA detected in any sample	n (%) ^b	X (X.X)	X (X.X)
HIV-1 RNA detected in at least 1 sample	n (%) ^b	X (X.X)	X (X.X)

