Participants with assessment at time of seroconversion	n (%) ^a	X (X.X)	X (X.X)
Participants with assessment after seroconversion (on IP)	n (%) ^a	X (X.X)	X (X.X)
Participants with assessment after seroconversion (after IP)	n (%) ^a	X (X.X)	X (X.X)
Participants without assessment at time of seroconversion	n (%) ^a	X (X.X)	X (X.X)
Population-based sequencing			
Participants with assessment prior to seroconversion	n (%) ^a	X (X.X)	X (X.X)
Plasma HIV-1 RNA ≥2000 cop/mL	n (%) ^b	X (X.X)	X (X.X)
Plasma HIV-1 RNA <2000 cop/mL, ≥200 cop/mL	n (%) ^b	X (X.X)	X (X.X)
Participants with assessment at time of seroconversion	n (%) ^a	X (X.X)	X (X.X)
Plasma HIV-1 RNA ≥2000 cop/mL	n (%) ^b	X (X.X)	X (X.X)
Plasma HIV-1 RNA <2000 cop/mL, ≥200 cop/mL	n (%) ^b	X (X.X)	X (X.X)
Participants with assessment after seroconversion (on IP)	n (%) ^a	X (X.X)	X (X.X)
Plasma HIV-1 RNA ≥2000 cop/mL	n (%) ^b	X (X.X)	X (X.X)
Plasma HIV-1 RNA <2000 cop/mL, ≥200 cop/mL	n (%) ^b	X (X.X)	X (X.X)
Participants with assessment after seroconversion (after IP)	n (%) ^a	X (X.X)	X (X.X)
Plasma HIV-1 RNA ≥2000 cop/mL	n (%) ^b	X (X.X)	X (X.X)
Plasma HIV-1 RNA <2000 cop/mL, ≥200 cop/mL	n (%) ^b	X (X.X)	X (X.X)

HIV-1 = Human immunodeficiency virus type 1

Percentages are calculated out of the number of participants (per IPM 027 treatment) ^a In the virology population ^b With data ^c With a population-based sequencing assessment

Table 14.3.7.12
 Overview of HIV-1 RNA and Genotyping Information Availability
 Virology Population

Statistic	IPM 027 Dapivirine (N=XXX)	IPM 027 Placebo (N=XXX)	IPM 032 Overall (N=XXX)
Population-based sequencing			
Participants without assessment at time of seroconversion	n (%) ^a	X (X.X)	X (X.X)
HIV-1 Subtype			
A1	n (%) ^c	X (X.X)	X (X.X)
C	n (%) ^c	X (X.X)	X (X.X)
Etc.	n (%) ^c	X (X.X)	X (X.X)

HIV-1 = Human immunodeficiency virus type 1

Percentages are calculated out of the number of the number of participants (per IPM 027 treatment) ^a In the virology population ^b With ^c With a population-based sequencing assessment

Table 14.3.7.13.1
Summary of Mutational Patterns of Resistance-Associated Mutations at Seroconversion Timepoint
Virology Population

Subgroup: All IPM 032 participants		Statistic	IPM 027 Dapivirine (N=XXX)	IPM 027 Placebo (N=XXX)	IPM 032 Overall (N=XXX)
Resistance-Associated Mutation Combination					
Number of successful assessments	n (%) ^a		X (X.X)	X (X.X)	X (X.X)
NNRTI mutations					
None	n (%) ^a		X (X.X)	X (X.X)	X (X.X)

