Any	n (%) ^b		X (X.X)	X (X.X)	X (X.X)
One	n (%) ^b		X (X.X)	X (X.X)	X (X.X)
Two	n (%) ^b		X (X.X)	X (X.X)	X (X.X)
Three	n (%) ^b		X (X.X)	X (X.X)	X (X.X)
...
Average	Mean		XX.X	XX.X	XX.X
NRTI mutations					
None	n (%) ^a		X (X.X)	X (X.X)	X (X.X)
Any	n (%) ^b		X (X.X)	X (X.X)	X (X.X)
One	n (%) ^b		X (X.X)	X (X.X)	X (X.X)
Two	n (%) ^b		X (X.X)	X (X.X)	X (X.X)
Three	n (%) ^b		X (X.X)	X (X.X)	X (X.X)
...
Average	Mean		XX.X	XX.X	XX.X
Major PI mutations					
None	n (%) ^a		X (X.X)	X (X.X)	X (X.X)
Any	n (%) ^b		X (X.X)	X (X.X)	X (X.X)
One	n (%) ^b		X (X.X)	X (X.X)	X (X.X)
Two	n (%) ^b		X (X.X)	X (X.X)	X (X.X)
Three	n (%) ^b		X (X.X)	X (X.X)	X (X.X)
...
Average	Mean		XX.X	XX.X	XX.X

Programmers Notes:

Please repeat table for the following subgroups: HIV-1 RNA level: HIV-1 RNA level: ≥ 2000 copies/mL, < 2000 copies/mL; HIV-1 subtype (C / Other) and Schedule A, B or C
- Table 14.3.7.13.2 will be similar to Table 14.3.7.13.1 but the heading and analysis will be based on Any Timepoint

HIV-1 = Human immunodeficiency virus type 1; NNRTI = Non-nucleoside reverse transcriptase inhibitor ; NRTI = Nucleoside reverse transcriptase inhibitor; PI = Protease inhibitor

Percentages are calculated out of the number of participants (per IPM 027 treatment) ^a In the virology population ^b Reported HIV-1 drug resistance-associated mutation

Resistance-associated mutations were defined using the Stanford HIV database algorithm Version 8.4

Table 14.3.7.14.1
Summary of Mutational Patterns of Resistance-Associated Mutations at Seroconversion Timepoint
Virology Population

Subgroup: All IPM 032 participants		IPM 027 Dapivirine (N=XXX)	IPM 027 Placebo (N=XXX)	IPM 032 Overall (N=XXX)
Mutation Score Classification	Statistic			
Resistance categorization score	N	XX	XX	XX
Susceptible				
Potential low-level resistant	n (%) ^a	X (X.X)	X (X.X)	X (X.X)
Low-level resistant	n (%) ^a	X (X.X)	X (X.X)	X (X.X)
Intermediate resistant	n (%) ^a	X (X.X)	X (X.X)	X (X.X)
High-level resistant	n (%) ^a	X (X.X)	X (X.X)	X (X.X)

Programmers Note:

Please repeat table for the following subgroups: HIV-1 RNA level: HIV-1 RNA level: \geq 2000 copies/mL, < 2000 copies/mL; HIV-1 subtype (C / Other); Schedule A, B or C
- Table14.3.14.2 will be similar to Table14.3.14.1 but the analysis and header will be based on Any Timepoint

HIV-1 = Human immunodeficiency virus type 1; NNRTI = Non-nucleoside reverse transcriptase inhibitor; NRTI = Nucleoside reverse transcriptase inhibitor; PI = Protease inhibitor

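### The SAP's Virology population includes women who stay HIV-negative, and the resistance tables use it as a denominator, with different denominators for the *None* and *Any* rows

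*SAP*

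**What the plan says.** SAP Section 5 builds the Virology population in two steps. The m-ITT population is the safety population minus women found to be infected at enrolment. Then: "The virology population includes all participants in the m-ITT population, with the exception of those participants who seroconverted after" the last product use visit. Neither step removes a woman who never seroconverts.

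Section 6.5 ties the endpoint to this set: "the primary virology analysis of drug resistance will be based on the virology population". Section 9.3.2 states the endpoint on a different base: "The proportion of HIV-1 seroconverters with at least one HIV-1 drug resistant mutation will be presented overall, and by research centre", with an exact 95% confidence interval. The same section expects incomplete genotyping, since one planned tabulation is "Reasons why a resistance test was not performed". It adds that "Only results at time of HIV-1 seroconversion will be included in tabulations".

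The shells in SAP Appendix 1 assign denominators as follows.

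- **Tables 14.3.7.13.1/2.** The first row, "Number of successful assessments", and the *None* rows carry footnote a. *Any*, *One*, *Two* and *Three* carry footnote b. The footnote line reads "In the virology population ^b Reported HIV-1 drug resistance-associated mutation".
- **Tables 14.3.7.14.1/2.** Every percentage shown carries footnote a, again the Virology population. Footnote b, successful assessments, is defined but no row uses it.

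The later virology addendum SAP, Section 3.2, uses the same population name for women who seroconverted during product use. Its Table 14.3.9.4.1 takes percentages of participants with a successful population-based genotype.

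**The concern.** A resistance percentage means something only among women who are infected and whose virus was sequenced. Here one population name has two meanings across the SAP and its addendum. The main SAP's meaning lets uninfected women into the denominator of tables that report secondary endpoint 2. Separately, *None* and *Any* should be complements among genotyped women, but the shell gives them different bases, so they cannot add to 100%.

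Resistance among women who become infected is a safety question for an antiretroviral ring, and the SAP Introduction says these analyses will go into regulatory submissions. The analysis is descriptive, so the printed percentages are the result.

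**Working it through.** **Inputs from the documents.** Anticipated enrolment is about 1400 (SAP 3.2). This agrees with 70% of the 1959 women randomised in IPM 027 (Protocol 1.4.2): 0.70 × 1959 = 1371. The documents state no number of seroconverters, genotypes or mutations, and no resistance percentage to reproduce.

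**Assumptions.** The Virology population is about 1400, and 10, 20 or 40 women seroconvert. For the example: 20 seroconverters, 18 genotyped, 5 with an NNRTI mutation and 1 more with an NRTI mutation only. That makes 6 mutation carriers and 18 − 5 = 13 genotyped women without an NNRTI mutation. Footnote b is read as women with a mutation of any class.

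**Step 1: scale of the footnote a error.** The factor is 1400/S, where S is the number of seroconverters: 1400/10 = 140, 1400/20 = 70, 1400/40 = 35. Against the 18 genotyped women it is 1400/18 = 77.8.

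**Step 2: the 9.3.2 proportion.** 6/20 = 30.0%, exact (Clopper-Pearson) 95% CI 11.9 to 54.3. This is unaffected by the shells.

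**Step 3: the shells as written, against women with a genotype.**

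| Row | As written | On 18 genotyped |
|---|---|---|
| 14.3.7.13.1 successful assessments | 18/1400 = 1.3% | – |
| 14.3.7.13.1 NNRTI *None* | 13/1400 = 0.9% | 13/18 = 72.2% |
| 14.3.7.13.1 NNRTI *Any* | 5/6 = 83.3% | 5/18 = 27.8% |
| 14.3.7.13.1 NRTI *Any* | 1/6 = 16.7% | 1/18 = 5.6% |
| 14.3.7.13.1 major PI *Any* | 0/6 = 0% | 0/18 = 0% |
| 14.3.7.14.1, one level holding the 5 NNRTI women | 5/1400 = 0.36% | 5/18 = 27.8% |

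**Step 4: do NNRTI *None* and *Any* add to 100%?**

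- Population of 1400: 0.9% + 83.3% = 84.3% (before rounding, 0.93 + 83.33).
- Population read as the 20 seroconverters: 13/20 = 65.0%, and 65.0% + 83.3% = 148%.
- Single denominator of 18: 72.2% + 27.8% = 100%.

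If footnote b is instead read class by class, NNRTI *Any* is 5/5 = 100% whatever the data show.

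**Step 5: does the note on tabulations repair this?** Limiting tabulations to results at seroconversion decides which results enter the numerator. It leaves the denominator named in the footnote unchanged.

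The body of Table 14.3.7.10 is not available in the text reviewed, so nothing here rests on it.

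**The case against.** The strongest reply is that everyone involved means seroconverters. Section 9.3.2 words the endpoint correctly. Tables 14.3.7.11 and 14.3.7.12 classify events relative to seroconversion, and the subgroup repeats by viral load and HIV-1 subtype are undefined for uninfected women. The addendum later defines the population properly, and its Table 14.3.9.4.1 re-tabulates NNRTI mutation counts on successful genotypes. Table 14.3.7.10 may also use a sound base, since its footnotes mention successful results. Apart from the 1400, every count in the example is assumed.

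Much of this is fair, and it limits the point. The endpoint sentence itself is not wrong, and counts and listings would let a reader recalculate. In Tables 14.3.7.13.1/2 a shrunken *None* does not hide resistance, and *Any* errs upward; of the two shell families only Tables 14.3.7.14.1/2 would understate it.

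What remains is that the intended meaning is not what the definition and footnotes say, and programmers work from those. The *None*/*Any* mismatch survives the charitable reading. The addendum covers neither the NRTI and major PI rows nor the resistance levels.

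It is also true that keeping the 9.3.2 proportion on all seroconverters counts ungenotyped women as having no mutation. That calls for showing their number, not for a mixed denominator.

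**Conclusion.** The concern holds. As written, the Virology population contains HIV-negative women. Tables 14.3.7.13.1/2 and 14.3.7.14.1/2 print percentages on it, and the first pair also mixes denominators within one block of rows. With a population of about 1400 and 10 to 40 seroconverters, the footnote a percentages are 140 to 35 times too small.

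The size depends on the assumed counts; the mismatch does not. The size of *Any* also depends on how footnote b is read. This should be fixed, because following the shells prints wrong percentages for a secondary endpoint. It does not affect the Section 9.3.2 proportion, and the underlying counts stay recoverable.

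**What to change.** 1. Replace the Section 5 definition with the one in addendum Section 3.2. This also corrects the footnote a rows of Tables 14.3.7.11 and 14.3.7.12.
2. In Tables 14.3.7.13.1/2 and 14.3.7.14.1/2, use participants with a successful genotype at the relevant timepoint as the one denominator for all mutation-count and resistance-level rows, as addendum Table 14.3.9.4.1 does.
3. Show beside it the number of seroconverters without a successful genotype (2 of 20 in the example).
4. Keep the Section 9.3.2 proportion on seroconverters and label both bases, because they differ when genotyping is incomplete: 6/20 = 30.0% against 6/18 = 33.3% (exact 95% CI 13.3 to 59.0).

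The cost is SAP wording and table footnotes. No new data are needed.
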